4.1.3 Method of assigning patients to treatment groups

An Interactive Response Technology (IRT) system will be used to screen eligible patients, perform drug assignment, register EoT and manage initial/re-supply ordering of drug supplies. The investigator will receive all necessary instructions to access the IRT from the Sponsor.

After the assessment of all in- and exclusion criteria, each eligible patient will receive treatment with nintedanib. The assigned dose of nintedanib will be based on the patient's weight at Visit 2 as shown in [Table 4.1.2: 1](#).

IRT will be used to assign medication numbers to eligible patients until EoT or premature discontinuation. Details of IRT procedures can be found in the IRT manual located in the Investigator Site File (ISF).

The appropriate medication numbers will be assigned and documented in the eCRF. Note that the medication number is different from the patient number (the latter is generated during screening via the IRT System).

4.1.4 Drug assignment and administration of doses for each patient

For an individual patient, the start of treatment period will be planned at Visit 2, and the end of treatment period is planned at the EoT Visit. The first dose of trial medication should be taken during the Visit 2 in the morning at the clinic and the last dose of trial medication should be taken in the evening before the EoT Visit.

During the treatment period, the treatment for an individual patient will be assigned via IRT contact during scheduled clinic visits detailed in the [Flow Chart](#).

Each patient will receive active drug at dosage of 150 mg bid, 100 mg bid, 75 mg bid, 50 mg bid or 25 mg bid. Nintedanib will be administered orally on a twice daily basis.

Based on the assigned dose, including possible dose reduction, the daily dose of trial medication will consist of 1 capsule (150 mg, 100 mg, or 25 mg strength) or 2 capsules (25 mg strength), or 3 capsules (25 mg strength) to be taken per os twice daily (b.i.d.) (see [Table 4.1.2: 1](#)).

Patients not able to swallow the 150 mg strength or the 100 mg strength capsule will have the possibility to take the 25 mg strength capsules (6 or 4 capsules per dose, respectively). To obtain kits with smaller capsules, an unscheduled visit should be registered in IRT.

At each concerned visit, the number of dispensed wallets will be adapted to assure sufficient coverage until the next dispensing visit.

The investigational product should only be dispensed to parents/caregiver(s) (or patients if applicable based on their maturity) by authorized personnel as documented in the "Trial Staff List".

In the event of force majeure or other disrupting circumstances (e.g. pandemic, war, please see [Section 6.1](#)), physical patient visits to the sites may not be feasible or may need to be restricted to ensure patient safety. Based on a thorough assessment of the benefits and risks,

the investigator may still decide to continue trial treatment. Where permitted by local law and regulations, trial medication may be shipped directly to the patients' home. If the defined minimum frequency of trial procedures cannot be adhered to, discontinuation from trial medication should be considered. (see [Appendix 10.9](#) for details).

The patient should take the capsules twice daily, at about the same time every day (between 06:00 and 11:00 in the morning, 18:00 and 23:00 in the evening), with a dose interval of approximately 12 hours from one dose to the next dose.

The patient should swallow the whole capsules with water (a glass, approximately 250 mL) and should not chew or crush the capsules. If contact with the content of the capsule occurs, hands should be washed immediately and thoroughly. As nintedanib may cause stomach discomfort, the patient is recommended to take the capsules with food, i.e. during or immediately before or after a meal.

In case a dose is forgotten, the dose should be skipped if the time window to the next dose is less than 8 hours. The next dose should be taken as scheduled. No catch up of missed doses is permitted.

In case of adverse events requiring a dose reduction between planned visits (see [Section 4.1.2](#) for details), the patient will attend an unscheduled visit. The investigator will visit the patient, record the reason for dose change, assign the new dose via IRT and instruct the patient/parent(s)/legal guardian on the number of capsules to be taken in the morning and in the evening until the next visit.

In case the start/end of an AE requires a dose reduction/increase without the need of a change in capsule size and without requiring a meeting with the investigator in person, the unscheduled visit for the patient can be replaced by a phone call. The investigator will register the phone call in IRT as an unscheduled visit and register the dose reduction/increase on the respective page in the eCRF.

Drug accountability will be completed carefully. Please refer to [Section 6.2.2](#) for instructions. If needed, an unscheduled visit can be registered in IRT at any time during the course of the trial to register a dose change, to obtain additional kit(s) or to obtain kits with smaller or larger capsules.

In case of adverse events requiring a dose interruption please refer to [Section 4.1.2](#) for instructions.

4.1.5 Blinding and procedures for unblinding

4.1.5.1 Blinding

In this open-label trial, treatment allocation will not be concealed throughout the trial. The eCRF will contain information on actual treatment.

For patients coming from InPedILD[®], the previous treatment received in InPedILD[®] part A (active drug or placebo) will remain unknown to the investigator and patient until after the

final database lock of InPedILD[®]. No individual unblinding regarding treatment received in InPedILD[®] should occur prior to this time.

4.1.5.2 Unblinding and breaking the code

Not applicable.

4.1.6 Packaging, labelling, and re-supply

The investigational medicinal products will be provided by BI or a designated CRO. They will be packaged and labelled in accordance with the principles of Good Manufacturing Practice (GMP). Re-supply to the sites will be managed via an IRT system, which will also monitor expiry dates of supplies available at the sites.

The investigational medicinal product, i.e. capsules containing nintedanib, will be packaged in blister cards. Blister cards will be packaged into one child-resistant tamper-evident wallet. Each wallet will be labelled with a multi-language booklet according to the requirements of the participating countries.

For details of packaging and the description of the label, refer to the ISF.

4.1.7 Storage conditions

Drug supplies will be kept in their original packaging and in a secure limited access storage area according to the recommended storage conditions on the medication label. A temperature log must be maintained for documentation.

If the storage conditions are found to be outside the specified range, the Clinical Research Associate (CRA) (as provided in the list of contacts) must be contacted immediately.

4.1.8 Drug accountability

The investigator or designee will receive the investigational drugs delivered by the sponsor or delegate when the following requirements are fulfilled:

- Approval of the clinical trial protocol by the IRB / ethics committee
- Availability of a signed and dated clinical trial contract between the sponsor or delegate and the investigational site,
- Approval / notification of the regulatory authority, e.g. competent authority,
- Availability of the curriculum vitae of the Principal Investigator,
- Availability of a signed and dated clinical trial protocol,
- Availability of the proof of a medical license for the Principal Investigator,
- Availability of FDA Form 1572.

Investigational drugs are not allowed to be used outside the context of this protocol. They must not be forwarded to other investigators or clinics. Patients should be instructed to return unused investigational drug.

The investigator or designee must maintain records of the product's delivery to the trial site, the inventory at the site, the use by each patient, and the return to the sponsor or warehouse /

drug distribution centre or alternative disposal of unused products. If applicable, the sponsor or warehouse / drug distribution centre will maintain records of the disposal.

These records will include dates, quantities, batch / serial numbers, expiry ('use-by') dates, and the unique code numbers assigned to the investigational medicinal product and trial patients. The investigator or designee will maintain records that document adequately that the patients were provided the doses specified by the Clinical Trial Protocol (CTP) and reconcile all investigational medicinal products received from the sponsor. At the time of return to the sponsor and / or appointed CRO, the investigator or designee must verify that all unused or partially used drug supplies have been returned by the clinical trial patient and that no remaining supplies are in the investigator's possession.

4.2 OTHER TREATMENTS, EMERGENCY PROCEDURES, RESTRICTIONS

4.2.1 Other treatments and emergency procedures

Rescue medications to reverse the action of nintedanib are not available.

████████████████████ during the trial will be recorded in the eCRF.

Treatment should be interrupted in case the patient experiences a weight decrease below 13.5 kg. Treatment can be resumed when patient's weight reaches the threshold of 13.5 kg.

If a patient experiences a drug related adverse event, the dose can be reduced to the next lower dose and the dose can be re-escalated after recovery.

The dose can be reduced without prior interruption, i.e. immediately stepping down from one dose to the next dose. If the reduced dose is well tolerated, re-escalation is possible within 4 weeks after dose reduction in case of AEs considered drug related, or within 8 weeks in case of AEs not considered drug related. If this occurs between scheduled visits, this will also require an unscheduled visit.

Only one reduced dose is possible for each body weight bin meaning that if patient is receiving already a reduced dose, no further dose reduction will be possible without re-increase before. Dose reduction and re-increase are allowed at multiple occasions.

The reduced dose per body weight bin is mentioned in [Table 4.2.1:1](#). This should be considered to manage adverse events. No further dose reduction outside of those listed will be allowed.

Temporary treatment interruption is also allowed to manage adverse events.

In case of pathological findings identified on follow-up bone imaging, or stunted growth identified on follow-up dental imaging, treatment should be interrupted, the patient case presented to the SMC by the sponsor and recommendations for next steps obtained.

Treatment may be resumed upon recommendation of the SMC.

In case of persistent adverse events observed at the reduced dose, or severe effects at the starting dose for new patients, permanent treatment discontinuation should be considered.

The criteria to be followed for treatment interruption, re-start and re-escalation are shown in [Table 4.2.1:1](#).

Table 4.2.1:1 Allowed treatment reduction / interruption periods

	AEs considered related to study drug	AEs or other events not considered related to study drug
Maximum interruption	4 weeks	8 weeks
Recommended restart of treatment	with reduced dose per Table 4.1.2: 1	with the same dose as before interruption
Re-escalation	re-escalation to the dose assigned per Table 4.1.2: 1 may occur any time per investigator judgement	n.a.

In case of pathological findings identified on follow-up bone imaging, or stunted growth identified on follow-up dental imaging, treatment should be interrupted, the patient case presented to the SMC by the sponsor and recommendations for next steps obtained. Treatment may be resumed upon recommendation of the SMC.

To manage diarrhoea and liver enzyme elevations guidelines similar to the parent trial and based on guidelines in adult programme are provided.

4.2.1.1 Management of diarrhoea

Diarrhoea is a known and the most frequent side effect of nintedanib treatment. However, potential causes for diarrhoea other than trial medication should always be considered and treated accordingly (e.g. viral infections, bacterial overgrowth, and antibiotic treatment). Diarrhoea should be managed as early as possible after onset of first symptoms with standard anti-diarrhoeal symptomatic treatment, e.g. loperamide.

If diarrhoea persists despite optimal symptomatic treatment, treatment interruption and/or dose reduction of nintedanib should be considered. [Table 4.2.1.1: 1](#) shows the recommendations for children and adolescents with the appropriate age and weight-adjusted dosing.

Table 4.2.1.1: 1 Management of diarrhoea (considered related to trial medication) in children and adolescents

Description	Symptomatic Treatment*	Action with trial medication
Diarrhoea with increase of <4 stools per day over baseline¹	
Initiate anti-diarrhoeal medicines at first signs of symptoms e.g. loperamide, as per the age-adjusted dosing regimen (Table 4.2.1.1: 2) until bowel movements cease for 12 hours.
 
Monitor for signs or symptoms of dehydration. Consider oral rehydration therapy.
	Continue same trial medication dose.
Diarrhoea with increase of 4 to 6 stools per day over baseline¹	
Initiate/continue anti-diarrhoeal medicines;
 
If diarrhoea of this severity persists for ≥48 to 72 hours assess for dehydration and electrolyte imbalance;
 
In addition, consider i.v. fluids and electrolyte replacement as clinically indicated.
	
If diarrhoea persists for ≥48 to 72 hours despite optimal symptomatic care:
 
 1. Interrupt trial medication until recovery. 2. Reduce dose to the next lower dose after recovery. 3. Re-escalate to the weight-adjusted dose within 4 weeks if deemed clinically appropriate.
Diarrhoea with increase of ≥7 stools per day over baseline¹; stool incontinence, or life threatening consequences	
Follow recommendations above.
 
In addition, consider stool work-up to exclude infectious colitis; adequate i.v. fluid replacement ≥24 hours, hospitalization as clinically indicated; consider referral to a GI specialist to rule out potential differential diagnoses.
	
 1. Interrupt trial medication until recovery. 2. Reduce dose to the next lower dose after recovery. 3. Consider re-escalation within 4 weeks to the weight-adjusted dose if deemed clinically appropriate. 
In case of reoccurrence of diarrhoea of this severity despite optimal symptomatic treatment and dose reduction, treatment with trial medication should be permanently discontinued.

Footnotes:

* Other potential causes for diarrhoea should always be considered and treated accordingly (e.g. viral infections, bacterial overgrowth, antibiotic treatment)

¹ Baseline defined as usual stools/day prior Visit 2.

Table 4.2.1.1: 2 Loperamide dose regimen based on group age

Group age	Posology
Children 6-8 years	One 5 ml (1 mg) dose three or four times daily with the duration limited to 3 days
Children 9-11 years	Two 5 ml (1 mg) doses four times daily with the duration limited to 5 days
Children 12-17 years	4 mg followed by 2 mg after each loose stool or every 2-4 hours to a maximum of 12 mg/day

4.2.1.2 Management of liver enzyme elevations

Nintedanib can be associated with increased liver enzymes. Concomitant use of other drugs known to cause liver enzyme elevations should be evaluated. For a detailed guidance on how to manage liver enzyme elevations, please refer to [Table 4.2.1.2: 1](#) for patients.

Table 4.2.1.2: 1 Recommendations for managing liver enzyme elevations

	AST or ALT increase to			Signs of hepatic injury*
	>1.5x to <3x ULN	≥3x to <5x ULN and no signs of hepatic injury	≥5x to <8x ULN and no signs of hepatic injury	
At Visit 2 for new patients (start of treatment)	Permanently discontinue trial medication or justify continuation ¹	Permanently discontinue trial medication	Permanently discontinue trial medication	Permanently discontinue trial medication
At any other Visit for new patients and At all visits for roll-over patients	Continue as planned ²	Reduce dose or interrupt trial medication ³	Interrupt trial medication	Interrupt trial medication (may subsequently need to be permanently discontinued ⁵)
		Close observation ⁴ After 2 weeks or any time later	Close observation ⁴ After 2 weeks or any time later	CLINICAL EVALUATION OF HEPATIC-INJURY
	<3x ULN	≥3x ULN	<3x ULN	≥3x ULN
	Reduced: return to initial dose. Interrupted: restart at reduced dose. Monitor every 2 weeks for at least 8 weeks	Permanently discontinue trial medication Close observation ⁴	Restart at reduced dose Monitor weekly for 4 weeks, then every 2 weeks for at least 8 weeks	Permanently discontinue trial medication. Close observation ⁴

Footnotes:

*Signs of hepatic injury are defined as

- ALT and/or AST ≥ 8 fold ULN
- ALT and/or AST ≥ 3 fold ULN and total bilirubin ≥ 2 fold ULN
- ALT and/or AST ≥ 3 fold ULN and unexplained INR >1.5
- ALT and/or AST ≥ 3 fold ULN and unexplained eosinophilia ($>5\%$)
- ALT and/or AST ≥ 3 fold ULN and appearance of fatigue, nausea, vomiting, right upper abdominal quadrant pain or tenderness, fever and/or rash

¹Investigator to confirm in writing that continuation is justified (e.g. intermittent fluctuation of transaminases).

²According to visit schedule. Consider additional control visits as adequate.

³To be decided by Investigator, based on individual risk assessment.

⁴Close observation: Re-test ALT and AST, alkaline phosphatase, total bilirubin, and eosinophils within 48 to 72 hours, then approximately 7 days, then approximately 2 weeks, preferably by using appropriate visit lab kit as instructed to site by the sponsor.

⁵Permanently discontinue after discussion with the sponsor if hepatic injury is a confirmed diagnosis and judged related to trial medication

Initial assessment of liver enzyme elevation should be performed at the investigational site. Blood samples for additional monitoring may be collected at the investigational site, primary care physician or external laboratory preferably with specific trial lab kits sent to the central laboratory for analysis or analysed locally.

4.2.1.3 Management of acute ILD exacerbations

In case of acute ILD exacerbations or clinical deterioration, all treatment options considered adequate by the Investigator are allowed. The patient may interrupt study treatment for up to 8 weeks, if necessary (e.g. if short-term full anticoagulation is performed).

4.2.2 Restrictions

4.2.2.1 Restrictions regarding concomitant treatment

As detailed in the exclusion criteria, new patients receiving nintedanib, full dose therapeutic anticoagulation or high dose antiplatelet therapy (e.g. acetyl salicylic acid >325 mg/day, or clopidogrel >75 mg/day, or equivalent doses of other antiplatelet therapy) are not eligible for participation in the study.

In case full-dose therapeutic anticoagulation or high-dose antiplatelet therapy is needed throughout the study, discontinuation of trial medication is highly recommended (see [Section 3.3.4.1](#)).

The use of nintedanib other than the investigational product is prohibited throughout the study, including the follow-up period (if any). If it is intended by a treatment discontinued patient to use available nintedanib outside the trial after trial treatment discontinuation, the patient should directly undergo the EoS visit 28 days after the EOT visit (no vital status will be required for this patient).

There are no restrictions for trial participants to receive vaccination for COVID-19 during or after study treatment period.

Cautionary notes

Nintedanib is a substrate of P-gp and, to a minor extent, CYP3A4. Co-administration with oral doses of a potent P-gp and CYP3A4 inhibitors, e.g. ketoconazole, erythromycin, may increase exposure to nintedanib. In such cases, patients should be monitored closely. Management of adverse reactions may require interruption, dose reduction, or discontinuation of therapy with nintedanib.

Co-administration with oral doses of a potent P-gp and CYP3A4 inducers, e.g. rifampicin, carbamazepine, phenytoin, and St. John's Wort may decrease exposure to nintedanib and should be avoided.

For reasons given above, the use of potent P-gp and CYP3A4 inhibitors and inducers is restricted as shown in [Table 4.2.2.1: 1](#).

Table 4.2.2.1: 1 Restrictions regarding use of potent P-gp and CYP3A4 inhibitors and inducers

P-glycoprotein (P-gp) and Cytochrome P450 3A4 (CYP3A4) inhibitors	
Ketoconazole, cyclosporine A (or ciclosporin), boceprevir, clarithromycin, conivaptan, erythromycin, indinavir, itraconazole, lopinavir, mibefradil, nefazodone, nelfinavir, posaconazole, ritonavir, saquinavir, telaprevir, telithromycin, voriconazole.	NOT permitted: 
P-gp and CYP3A4 strong inducers	
Avasimibe, carbamazepine, phenytoin, rifampin	NOT permitted: 
Products including St. John's wort	NOT permitted: 

As the most common side effects known for nintedanib are GI effects i.e. diarrhoea, nausea and vomiting (see [Section 1.4.2](#)) the concomitant use of medication with an overlapping safety profile (e.g. mycophenolate mofetil) should be carefully considered.

Nintedanib is also associated with increases in liver enzymes and bilirubin. If in addition to the trial medication, a treatment is introduced that is known to induce AST/ALT elevations (e.g. methotrexate, bosentan), additional measurements of liver enzymes (ALT and AST, alkaline phosphatase, total bilirubin, and eosinophils) every 2 weeks for approximately 6 weeks, preferably by using intermediate (a-visit) trial lab kit are recommended.

Patients who are using a bronchodilator must have their spirometry performed according to the guidelines provided below:

- Withhold short-acting bronchodilators for at least 8 hours before the assessments,
- Withhold long-acting bronchodilators for at least 24 hours before the assessments.

In case of a patient forgets to withhold bronchodilator(s) intake in the morning of clinic visits, the study visit has to be rescheduled the day after.

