Test results must be documented in the patient's pregnancy test diary card and will be transferred to the patient's records by site staff at the next site visit. In case of positive results, procedures defined in [Section 5.2.7.2.3](#) should be followed.

At 'a-Visits', safety blood, and urine samples will be collected and submitted to the central laboratory if needed for additional safety monitoring at the discretion of the Investigator (see cautionary notes under [Section 4.2.2.1](#) for additional safety monitoring). Safety laboratory parameters to be assessed at regular visits are listed in [Table 5.2.3:1](#) Safety laboratory parameters to be assessed at these additional visits are listed in [Table 5.2.3:2](#).

The samples may be collected at the office of a local doctor using preferably trial specific lab kits that will be sent to a central laboratory for analyses or may be analysed locally. These kits will be provided to patients at study visits as applicable. Around 2.5 mL will be taken at each a-Visit.

If laboratory values indicate abnormality, adequate and more frequent blood sampling may be performed at the discretion of the Investigator.

In case of liver function value elevations, close monitoring must be ensured by the Investigator. Refer to [Section 4.1.2](#) for monitoring elevations and [Section 3.3.4](#) for withdrawal criteria.

In case the criteria for hepatic injury are fulfilled, a number of additional measures will be performed (please see [Section 5.2.7.1](#) and the DILI Checklist provided in the eDC system). The amount of blood taken from the patient concerned will be increased due to these additional samplings.

The central laboratory will transfer the results of the analysis to the sponsor or delegate.

Table 5.2.3:1 Safety laboratory tests at scheduled site visits

The laboratory tests at regular site visits will include:

Functional lab group	Test name
Haematology	Haematocrit Haemoglobin Red blood cells (RBC) White blood cells (WBC) Platelet count Mean corpuscular volume (MCV)
Automatic WBC differential (relative and absolute)	Neutrophiles total Lymphocytes total Eosinophiles Basophiles

Functional lab group	Test name
	Monocytes Lymphocytes
Manual differential WBC (if automatic differential WBC is abnormal)	Polymorphonuclear neutrophils (segs), band neutrophils (stabs), eosinophils, basophils, monocytes, lymphocytes
Coagulation	Activated partial thromboplastin time (aPTT) Prothrombin Time (PT) INR

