Enzymes	Aspartate aminotransferase (AST) Alanine aminotransferase (ALT) Alkaline phosphatase (AP) Gamma glutamyl transferase (GGT) Creatine kinase (CK) Lactate dehydrogenase (LDH)
Substrates	Glucose (non fasting, V1 and V2 only) Creatinine eGFR (V1 and V2 only) Uric Acid Total bilirubin Direct bilirubin Total protein Thyroid stimulating hormone
Electrolytes	Calcium Sodium Potassium Chloride Phosphate
Serum Pregnancy test (in all female subjects) at all scheduled visits requiring blood sampling for laboratory tests and if urine pregnancy test is positive	Human Serum Chorionic Gonadotropin
Urine Pregnancy test (dipstick) (Locally provided for use between scheduled clinic visits to assure pregnancy test every 4 weeks)	Human Chorionic Gonadotropin in the urine
Urinalysis macro panel	Semi-quantitative: Urine nitrite Urine protein Urine glucose Urine Blood Urine leukocyte esterase Urine pH

Table 5.2.3:2 Safety laboratory tests at intermediate ‘a’-visits

The laboratory tests at intermediate ‘a’-visits will include:

Functional lab group	Test name
Enzymes	Aspartate aminotransferase (AST) Alanine aminotransferase (ALT)

Functional lab group	Test name
	Alkaline phosphatase (AP) Gamma glutamyl transferase (GGT)
Substrates	Creatinine Total bilirubin Total protein
Electrolytes	Calcium Sodium Potassium Chloride Phosphate
Urinalysis	Semi quantitative: Urine nitrite Urine protein Urine glucose Urine Blood Urine leukocyte esterase Urine pH

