5.2.7.1.4 Adverse events of special interest

The term adverse events of special interest (AESI) relates to any specific AE that has been identified at the project level as being of particular concern for prospective safety monitoring and safety assessment within this trial, e.g. the potential for AEs based on knowledge from other compounds in the same class. AESIs need to be reported to the sponsor’s Pharmacovigilance Department within the same timeframe that applies to SAEs, please see [Section 5.2.7.2.2](#).

The following are considered as AESIs:

- adverse events relating to gastrointestinal perforation
- bleeding
- hepatic injury.
- pathological findings identified on bone imaging
- stunted growth identified on dental imaging.

Hepatic injury

In this trial protocol, signs of hepatic injury are defined as:

- ALT and/or AST ≥ 8 fold ULN
- ALT and/or AST ≥ 3 fold ULN and total bilirubin ≥ 2 fold ULN*
- ALT and/or AST ≥ 3 fold ULN and unexplained INR $> 1.5^*$
- ALT and/or AST ≥ 3 fold ULN and unexplained eosinophilia ($>5\%$)*
- ALT and/or AST ≥ 3 fold ULN and appearance of fatigue, nausea, vomiting, right upper abdominal quadrant pain or tenderness, fever and/or rash

*in the same blood draw sample.

These lab findings constitute a hepatic injury alert and the patients showing these lab abnormalities need to be followed up according to the “DILI checklist” provided in the eDC system.

In case of clinical symptoms of hepatic injury (icterus, unexplained encephalopathy, unexplained coagulopathy, right upper quadrant abdominal pain, etc.) without lab results (ALT, AST, total bilirubin) available, the investigator should make sure these parameters are analysed, if necessary, in an unscheduled blood test. Should the results meet the criteria of hepatic injury alert, the procedures described in the DILI checklist should be followed.

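### The a-visit kit that Protocol Section 4.2.2.1 prefers covers four of the five liver tests it recommends, because Table 5.2.3:2 has no eosinophil count

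*Protocol*

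**What the plan says.** Protocol Section 4.2.2.1 deals with co-medication that can raise transaminases and gives methotrexate and bosentan as examples. It recommends extra liver monitoring: "ALT and AST, alkaline phosphatase, total bilirubin, and eosinophils) every 2 weeks for approximately 6 weeks, preferably by using intermediate (a-visit) trial lab kit".

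Protocol Section 5.2.3 describes the a-visits. Samples are taken "if needed for additional safety monitoring at the discretion of the Investigator (see cautionary notes under", and the reference that follows is to Section 4.2.2.1. The same section states: "Safety laboratory parameters to be assessed at these additional visits are listed in" Table 5.2.3:2. That table opens with "The laboratory tests at intermediate ‘a’-visits will include" and then lists enzymes, substrates, electrolytes and urinalysis. The entry "Automatic WBC differential (relative and absolute"), which contains eosinophils, stands in Table 5.2.3:1 for scheduled visits.

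Two other places use eosinophils for liver safety:

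- Section 5.2.7.1.4 counts transaminases of at least three "fold ULN and unexplained eosinophilia" (above 5%) as a sign of hepatic injury, with both findings "in the same blood draw sample". SAP Section 5.4.4 repeats this rule and summarises the proportion of patients with such signs.
- Footnote 4 of Table 4.2.1.2:1 defines close observation after an elevation: "Re-test ALT and AST, alkaline phosphatase, total bilirubin, and eosinophils within 48 to 72 hours, then approximately 7 days, then approximately 2 weeks".

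**The concern.** Two rules in the same protocol disagree. One names eosinophils and prefers the a-visit kit. The other defines the a-visit panel without them. A site that follows both would not run a test the protocol names for liver safety in children, and nothing in either section tells it to add a tube.

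The count has a use. Between 3x and 5x ULN with no sign of hepatic injury, Table 4.2.1.2:1 lets the investigator choose between dose reduction and interruption. With a sign, it calls for interruption and a clinical evaluation, with possible permanent discontinuation. A sign also triggers the DILI checklist and reporting as an adverse event of special interest. What is at stake is prompt recognition of one route to that alert.

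**Working it through.** The protocol states no coverage figure to reproduce, so the check is a comparison of lists followed by simple counts.

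**1. Recommended tests (Section 4.2.2.1) against the a-visit panel (Table 5.2.3:2)**

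| Test | In Table 5.2.3:2? |
|---|---|
| ALT | yes |
| AST | yes |
| Alkaline phosphatase | yes |
| Total bilirubin | yes |
| Eosinophils | no |

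Coverage is 4 of 5. The table also holds GGT, creatinine, total protein, five electrolytes and urinalysis, but no haematology or coagulation group. It shows no redaction.

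**2. Signs of hepatic injury (Section 5.2.7.1.4) assessable on an a-visit panel alone**

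| Sign | Assessable? |
|---|---|
| ALT and/or AST at least 8x ULN | yes |
| At least 3x ULN with total bilirubin at least 2x ULN | yes |
| At least 3x ULN with unexplained INR above 1.5 | no, INR is only in Table 5.2.3:1 |
| At least 3x ULN with unexplained eosinophilia above 5% | no, the differential is only in Table 5.2.3:1 |
| At least 3x ULN with listed symptoms | yes, needs no further laboratory test |

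Two of 5 signs cannot be assessed. Only the eosinophil gap conflicts with Section 4.2.2.1, because that section does not ask for INR.

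**3. Results missing per course**

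Sampling every 2 weeks for approximately 6 weeks gives 6 / 2 = about 3 samples. If all use the a-visit panel and none has a local differential, about 3 eosinophil results are missing. That is the upper end. After week 12, scheduled visits are 12 or 16 weeks apart in the Flow Chart, and their panel includes the differential. If the new drug starts at a random point between visits (an assumption), a 6-week course contains a scheduled visit with probability 6/16 = 37.5% to 6/12 = 50%.

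**4. What a missing count changes, by enzyme level**

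- Below 3x ULN: nothing. Every sign requires at least 3x ULN.
- From 3x to below 5x ULN: it may decide between a choice of reduction or interruption and mandatory interruption with evaluation, if no other sign is present.
- From 5x to below 8x ULN: the drug is interrupted either way. The count may decide whether the case is a hepatic-injury alert.
- At 8x ULN or above: nothing, because the enzyme level is itself a sign.

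**5. Blood volume**

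Section 5.2.3 gives about 6.1 mL for a scheduled visit and about 2.5 mL for an a-visit. The difference is 6.1 - 2.5 = 3.6 mL per sample. Over 3 samples this is 3 x 3.6 = 10.8 mL. At the 13.5 kg minimum entry weight it is 10.8 / 13.5 = 0.8 mL/kg, the extreme case.

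**The case against.** The strongest reply is that the protocol leaves several ways to obtain the count. The monitoring is recommended, not required, and the kit is only preferred. Sections 5.2.3 and 6.2.2 allow local analysis. Section 5.2.3 also allows more frequent sampling when values are abnormal, and the wording of Table 5.2.3:2 does not forbid an added test. From 3x ULN, footnote 4 of Table 4.2.1.2:1 asks for eosinophils. The Laboratory Manual, which is not among the documents, may describe a kit that already includes a differential.

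All of this stands as a limit on the consequence. None of it puts eosinophils in the a-visit panel. A local differential helps only if someone notices the omission and orders it. If the kit does contain a differential, Table 5.2.3:2 is incomplete and still needs correcting. The footnote 4 re-test has limits too. It leaves the choice of kit to the sponsor's instruction, so the gap could recur. It is also a new draw: if enzymes have fallen below 3x ULN by then, the same-draw sign cannot be established for the first sample.

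A reader might also infer more than the documents support:

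- That every course loses all its eosinophil results. This holds only if no scheduled visit falls in the period and no local differential is run.
- That recognition is delayed by 2 to 3 days. The 48 to 72 hours is the re-test window. The protocol gives no time to result.
- That this gap alone keeps the a-visit from covering the hepatic-injury definition. INR is absent as well and Section 4.2.2.1 does not request it, which suggests this monitoring was not built to complete the definition in one draw.

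**Conclusion.** The inconsistency is confirmed from the text: the preferred kit, as its panel is listed, omits one of the five tests recommended with it. On a sample run with that panel alone, the eosinophilia and INR signs cannot be assessed (2 of 5). Up to about 3 eosinophil results per course would be missing.

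The effect is minor. It is confined to enzyme values from 3x to below 8x ULN with no other sign present, and mainly to 3x to below 5x ULN, where the drug action can differ. The enzyme rise itself is still seen on the a-visit panel. The primary endpoint does not depend on this panel. The number of patients affected cannot be estimated, because the documents do not say how many will start such a drug. The conclusion rests on Table 5.2.3:2 being the full a-visit panel, as Section 5.2.3 presents it. What the kits contain in practice cannot be checked here.

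**What to change.** Either change resolves the conflict:

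- Add the white-cell differential (eosinophils) to Table 5.2.3:2 and update the Laboratory Manual to match. This reaches every a-visit, whatever its reason.
- State in Section 4.2.2.1 that this monitoring uses a kit with a differential, such as the scheduled-visit kit. This reaches only patients starting a hepatotoxic drug, and the scheduled-visit kit would also supply INR.

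It would help to name the kit in footnote 4 of Table 4.2.1.2:1 at the same time, so that the re-test does not repeat the gap.

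The drafting cost is one table row or one sentence. The cost to patients is some extra blood, which matters because Section 5.2.3 asks for the smallest feasible volume. With the scheduled-visit kit it is at most about 3.6 mL per sample. The documents give no volume for a differential alone, and the first option applies to more visits, so which option uses less blood overall cannot be determined.
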